11.3.3. Efficacy Analysis Population

The efficacy analysis population will include all enrolled patients who receive any amount of andexanet treatment, undergo surgery, and have a baseline anti-fXa activity analyzed by central laboratory at or above the evaluability threshold (75 ng/mL for apixaban, edoxaban and rivaroxaban, and 0.25 IU/mL for enoxaparin).

11.4. Baseline and Demographic Characteristics

Baseline and demographic characteristics will be summarized for all populations listed above. Data will be summarized using descriptive statistics of frequencies for categorical data and means, medians, standard deviations, minimums, and maximums for continuous data. No inferential analyses of these data are planned.

11.5. Efficacy Endpoints and Analyses

11.5.1. Definitions

Hemostasis will be assessed from the start of surgery to the end of the procedure. Categories for the assessment of intraoperative hemostasis are provided in Table 3.

Table 3: Intraoperative Hemostasis Categories

Category	Definition
Excellent	Normal hemostasis during the procedure
Good	Mildly abnormal hemostasis as judged by quantity or quality of blood loss (e.g., slight oozing from surgical wounds)
Moderate	Moderate abnormality in intraprocedural hemostasis (e.g., controllable bleeding) but no need for additional systemic procoagulant products *
Poor	Severe hemostatic abnormality during the procedure (e.g., severe refractory hemorrhage) and need for additional systemic procoagulant products *

* Tranexamic acid excluded.

The evaluation period for anti-fXa activity covers the period of time from 5 minutes following the end of the andexanet bolus to just prior to the end of the andexanet infusion. The baseline measurement will be the last value obtained prior to andexanet treatment.

The hemostasis evaluation would exclude unexpected blood loss due to surgical complications that may cause uncontrolled bleeding, such as unintended injury of a major vessel or parenchymal tissue.

11.5.2. Efficacy Endpoints

11.5.2.1. *Primary Efficacy Endpoint*

The primary efficacy endpoint is the achievement of effective hemostasis, as determined by the surgeon's assessment of intraoperative hemostasis and confirmed by adjudication by an independent EAC (see Table 3).

For each patient, hemostasis will be considered to be effective if the intraoperative hemostasis category is Excellent or Good, and ineffective if the intraoperative hemostasis category is Moderate or Poor.

A patient will be deemed non-evaluable if s/he meets the criteria specified in the EAC Charter.

11.5.2.2. *Secondary Efficacy Endpoint*

The secondary efficacy endpoint is the percent change in anti-fXa activity from baseline to the evaluation period nadir. The evaluation period starts 5 minutes after the end of the andexanet bolus and ends just prior to the end of the andexanet infusion.

Patients who do not have at least 1 anti-fXa activity level within the evaluation period will have percent decrease imputed as 0.0% (i.e., using the baseline value as the nadir value).

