10.4. Intraoperative and Hospitalization Assessments

10.4.1. Surgical Intervention

All patients entering the trial are required to have an urgent need for surgical intervention. Institutional or procedural consents should be administered for the surgical intervention in accordance with local requirements and in addition to the study specific informed consent.

- The start of surgery is the initial incision.
- The end of surgery is final skin closure.

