10.4.2. Intraoperative Blood Loss

Investigators will report blood loss during surgery for each patient. Blood loss will be reported as an estimate of blood loss in milliliters. Blood loss will be reported at the end of surgery. It is an intraoperative assessment and will not be updated for post-closure blood loss.

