7.3 Post-Surgical Bleeding and Rescue Therapy	In this study, there is potential for patients to require additional andexanet treatment beyond what is stipulated for patients, due to post-surgical bleeding events. Investigators will therefore be allowed to deliver a second dose of andexanet as rescue therapy should such a situation arise. If rescue re dosing is deemed necessary, Investigators will be required to document in the CRF the clinical justification for why	In this study, there is potential for patients to require additional andexanet treatment beyond what is stipulated for patients during surgery , due to post-surgical bleeding events. Investigators will therefore be allowed to deliver a second dose of andexanet (low-dose bolus + 120 minute infusion only) as rescue therapy should such a situation arise. If rescue re dosing is deemed necessary,	Added text to clarify when and how a second dose of andexanet shall be delivered, and to further clarify the criteria for poor hemostatic	NS

	subjects require additional dosing of andexanet. Re dosing procedures will mirror those required for the initial andexanet dosing. Please refer to Appendix A for the timing of extended infusion or re-dosing of andexanet in surgical patients. The decision criteria for re-dosing are outlined in Section 6.2.	Investigators will be required to document in the CRF the clinical justification for why subjects require additional dosing of andexanet. Re-dosing procedures will mirror those required for the initial andexanet dosing. Please refer to Appendix A for the timing of extended infusion or re-dosing of andexanet in surgical patients. The decision criteria for re-dosing are outlined in Section 6.2. If a patient is confirmed to have post-surgical bleeding by the EAC, then they will be considered to have poor hemostatic efficacy (irrespective of the treatment given for bleeding, if any).	efficacy.	
10	N/A	Assessments, testing and treatment schedules are detailed in Appendix A. No reference to timing or frequency is described below.	Language added for clarity.	NS
10.1 Baseline Assessments	N/A	Baseline Assessments	Section added to provide information on assessments performed at Baseline	S

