3.5. Safety Plan and Monitoring

The study will be conducted in patients who, by virtue of their condition, will typically be hospitalized or will be seen initially in the emergency department. As such, treatment with andexanet and subsequent monitoring will be done in a medical setting. It is expected that patients requiring urgent surgery will remain hospitalized for at least 12 hours, the timeframe for the primary efficacy evaluations. During the first 12-hour period (Study Day 1), AEs, vital signs, physical examinations, and laboratory testing will be performed as indicated in [Appendix A](#) to monitor safety. Survival status will be ascertained on Study Day 30, and cause of death will be recorded. Antibody samples will be taken at baseline and Day 30 to assess immunogenicity against andexanet, FX, FXa, and host-cell proteins (HCPs).

Of the 352 patients, 9.7% of patients with acute major bleeding in ANNEXA-4 experienced protocol-defined, adjudicated TEs that occurred within 30 days of andexanet treatment. While the attributability of these events to andexanet is uncertain, it is significantly possible that they will occur in the current study, given the anticipated enrolled population, for which reversal of anticoagulation may expose the underlying risk of TEs, and andexanet's known effects on coagulation biomarkers such as D-dimer, F1+2, and TFPI. In this study, patients with TEs within 30 days of Screening, those with a history of hypercoagulable states, and those who received procoagulant products within 7 days of Screening will not be eligible for the study due to their much greater risk for TEs in general and following anticoagulation reversal. In this study, TEs will be considered AEs of special interest (AESIs) and will be reported within 24 hours to the Sponsor. Thrombotic events, both suspected and confirmed by adjudication, will be tracked as safety endpoints for the study. To mitigate the risk of TEs, Investigators are encouraged to consider resumption of an anti-thrombotic agent as soon as it is clinically appropriate.

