7.2.2. Blood Products

To maintain uniformity in transfusion practices across study participants, it is strongly suggested that the trigger for PRBC transfusion is hemoglobin ≤ 8.0 g/dL (± 1 g/dL). The hemoglobin triggering a transfusion, clinical stability factors (e.g., shock) influencing the decision to transfuse, as well as the number of units transfused should be recorded on the CRFs.

Whole blood and platelet transfusions may be administered according to standard institutional/local practices and/or guidelines. Investigators may consider using pro-coagulant factor infusions (e.g., 3- or 4-factor PCC/activated PCC, rfVIIa, plasma, fresh frozen plasma [FFP]) per their judgement in case of hemodynamic necessity. Otherwise, treatment with the above products is strongly discouraged, though not prohibited, during the entire 30-day observation period.

Use of procoagulant factor infusions (e.g., 3- or 4-factor PCC/activated PCC, rfVIIa, plasma, FFP) and whole blood intraoperatively or within 12 hours following surgery will result in the patient being considered having poor hemostatic efficacy (see [Table 3](#)) with andexanet.

Use of blood products, including number of units transfused and the date and time of administration should be recorded on the CRFs.

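### Amendment 1 appears to carry two scoring rules for the primary endpoint: Section 11.5 counts intraoperative hemostasis only, while the logged addition to Section 7.3 makes any adjudicated post-surgical bleed a poor result

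*Protocol*

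**What the plan says.** Amendment 1 sets the primary endpoint in Section 11.5. Section 11.5.1 fixes the window: "Hemostasis will be assessed from the start of surgery to the end of the procedure". Section 10.4.1 closes that window: "The end of surgery is final skin closure". Section 11.5.2.1 then states that "hemostasis will be considered to be effective if the intraoperative hemostasis category is Excellent or Good", and that Moderate or Poor is ineffective. Table 3 defines all four categories by what happens during the procedure. In the same spirit, Section 10.4.2 says of the blood-loss estimate: "It is an intraoperative assessment and will not be updated for post-closure blood loss". Section 11.5.2.3 lists post-surgical major bleeding by ISTH criteria, within 12 hours after the end of surgery, as a separate exploratory endpoint.

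Appendix G compares the original protocol with Amendment 1. Its new text for Section 7.3 adds: "If a patient is confirmed to have post-surgical bleeding by the EAC, then they will be considered to have poor hemostatic efficacy". The rule is to apply however the bleed is managed, even if nothing is given for it. The log gives clarification of the criteria for poor hemostatic efficacy as part of its reason, and classes the change as non-substantial.

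The original protocol has a similar tension. Its Section 7.2.2 says that procoagulant factor infusions and whole blood given "intraoperatively or within 12 hours following surgery will result in the patient being considered having poor hemostatic efficacy", with a cross-reference to Table 3. Its Section 3.5 expects patients to stay in hospital "for at least 12 hours, the timeframe for the primary efficacy evaluations". Its Sections 11.5.1 and 11.5.2.1 nevertheless end the assessment with the procedure and score intraoperative hemostasis.

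**The concern.** The two rules give opposite results for one identifiable kind of patient: Excellent or Good at closure, then a bleed confirmed by the Endpoint Adjudication Committee (EAC). The Section 7.3 rule is also wide. It covers any confirmed post-surgical bleed, whereas the exploratory endpoint covers major bleeds within 12 hours. Section 11.7.1 has the EAC assess all potential post-surgical bleeds and record whether anticoagulation had been restarted. Read literally, then, a late bleed after re-anticoagulation would turn a good operation into a primary-endpoint failure.

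This proportion is the only primary endpoint, and Section 11.6 justifies the efficacy sample size by its precision. In an open-label single-arm study the estimate has no control arm to absorb a change in definition, so any difference in scoring goes straight into the reported result.

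**Working it through.** **Do the two rules concern the same variable?**

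- The Section 7.3 sentence is absent from the original Section 7.3, so it is an addition. It cannot be deleted text whose strikethrough was lost in conversion.
- Section 7.3 speaks of hemostatic efficacy, while amended Section 11.5.2.1 speaks of effective hemostasis. The amendment uses the terms interchangeably. Its logged study-design text has the surgeon assess hemostatic efficacy at skin closure. Its logged sample-size text attaches excellent or good to hemostatic efficacy, where Section 11.6 attaches the same words to hemostasis. The exploratory endpoint relating the outcome to anti-fXa activity says hemostatic efficacy in the log and intraoperative hemostasis in Section 11.5.2.3.
- Section 12.0 has the EAC adjudicate hemostatic efficacy, and no second endpoint of that name is defined.
- Poor is a Table 3 category, and Section 11.5.2.1 counts it as ineffective.

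**One patient under both rules**

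| Patient | Section 11.5.2.1 | Logged Section 7.3 |
|---|---|---|
| Good at closure, no later bleed | Effective | Effective |
| Good at closure, later EAC-confirmed bleed | Effective | Poor, so ineffective |
| Moderate or Poor at closure | Ineffective | Ineffective |

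**The plan's own precision figures.** Inputs from Section 11.6: 200 enrolled and 10% to 25% attrition, so 200 × 0.90 = 180 and 200 × 0.75 = 150. Half-width = 1.96 × √(p(1 − p)/n). At p = 0.5:

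- n = 150: 1.96 × √(0.25/150) = 8.0 points
- n = 180: 1.96 × √(0.25/180) = 7.3 points

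These agree with the stated 8% and 7.3%. At the rates used below:

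- p = 0.77: 6.7 points (n = 150) and 6.1 points (n = 180)
- p = 0.80: 6.4 points (n = 150) and 5.8 points (n = 180)

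**Size of the conflict.** Let p be the success rate under Section 11.5.2.1 and q the share of those successes with a later EAC-confirmed bleed. The rate under Section 7.3 is p(1 − q), and the fall is p × q. The 77% is the rate assumed in the original protocol's superseded power calculation and serves only as an illustration; 80% is an assumption. The documents give no value for q, so a range is shown.

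| q (assumed) | p = 77%: rate (fall) | p = 80%: rate (fall) |
|---|---|---|
| 2% | 75.46% (1.54 points) | 78.4% (1.6 points) |
| 5% | 73.15% (3.85 points) | 76.0% (4.0 points) |
| 10% | 69.30% (7.70 points) | 72.0% (8.0 points) |
| 15% | 65.45% (11.55 points) | 68.0% (12.0 points) |

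The fall equals the half-width when q = half-width / p. For p = 0.77 that is 6.15/77 = 8.0% at n = 180 and 6.73/77 = 8.7% at n = 150. At p = 0.77 and n = 180, q of 2%, 5% and 10% reclassifies about 3, 7 and 14 patients (180 × 0.77 × q).

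**The case against.** The strongest reply is that the visible body of Amendment 1 is consistent. Section 11.5 is intraoperative throughout, post-surgical bleeding is listed separately both as an endpoint and in the EAC remit, and an endpoint section should outrank a rescue-therapy section. The competing sentence is seen only in the change log, and that log is not an exact copy of the body. For Section 10.2.1, its new-text column carries a condition about the dosing time being known that the amended body lacks. This stands in part: the body of Section 7.3 has to be checked, and it limits confidence to moderate. It does not dispose of the point. The log entry describes the same amendment that contains the Section 11.5 rule, so this is not a comparison of current with superseded text, and its stated purpose is to define a poor result.

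A reader might infer further that current Section 7.2.2 contradicts Table 3, so that a Good-rated patient given plasma is both a success and a failure. The documents do not support that. The quoted Sections 7.2.2 and 3.5 belong to the original protocol. The log says words were removed from Section 7.2.2, but the deletion marks are lost, so what survives cannot be read. The Section 3.5 phrase is a remark about hospital stay. Both show only that a similar ambiguity existed before the amendment.

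A reader might also infer that the EAC cannot adjudicate, or that the definition will be picked after the data are seen. The EAC Charter is not shown and may settle the matter. What can be said is that, for the primary endpoint, Section 11.5.2.1 refers only non-evaluability to that Charter, and that no protocol text shown ranks the two rules.

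**Conclusion.** The point holds with moderate confidence. As documented, Amendment 1 has an intraoperative rule in Sections 11.5.1 and 11.5.2.1 and a post-surgical override in the logged text of Section 7.3. They score the same patient in opposite ways. It is a conflict of definition; the sample-size figures reproduce and are not in dispute.

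Its size depends on a bleeding rate that the documents do not give. Over an assumed 2% to 15% and intraoperative success of 77% to 80%, the primary rate falls by about 1.5 to 12 points. At the low end this is well inside the half-width of about 6 to 7 points; above roughly 8% to 9% (at 77% success) it exceeds it. It would therefore be too strong to say that the conflict must outweigh sampling error. It is enough that it could, and that the reported result should not depend on which section is read.

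**What to change.** Check the body of amended Section 7.3, then reconcile it, and any post-surgical window left in Sections 7.2.2 and 3.5, with Section 11.5.2.1 so that one scoring rule applies.

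- **Simplest course.** State in Section 11.5.2.1 that the primary endpoint is the intraoperative category alone and that Section 7.3 does not alter it. Report one prespecified supportive analysis in which success means intraoperative Excellent or Good and no EAC-confirmed post-surgical major bleed within 12 hours of the end of surgery.
- **If the sponsor means the Section 7.3 rule to count.** Write it into Section 11.5 with its time window and severity threshold.

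In either case, align the EAC Charter. The cost is wording changes and one extra table. The intraoperative category and the adjudicated bleeds are already collected, so no new data are needed.

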11.5.2.3. Exploratory Efficacy Endpoints

The following efficacy endpoints will be analyzed as exploratory:

- Relationship between intraoperative hemostasis and anti-fXa activity.
- Anti-fXa activity as measured by additional parameters, including, but not limited to: on-treatment nadir, absolute change from baseline to on-treatment nadir, number of patients with percent reduction from baseline > 80%.
- Reversal of anticoagulant effect as measured by TG parameters (with ETP as the primary measure).
- Occurrence of receiving 1 or more RBC transfusions from start of the andexanet bolus through 12 hours after the end of surgery.
- The number of RBC units transfused per patient from the start of the andexanet bolus through 12 hours after the end of surgery.
- The use of non-RBC, non-platelet blood products and/or hemostatic agents (both systemic and topical) through 12 hours after the end of surgery.
- Transfusion-corrected change in hemoglobin from baseline to nadir within 12 hours after the end of surgery.
- Time from the signing of informed consent to the start of surgery.
- Time from clinical presentation at treatment facility to the start of surgery.
- Length of index hospitalization, assessed at the Day 30 visit.
- Time hospitalized in a PACU, assessed at the Day 30 visit.
- Time hospitalized in an ICU, assessed at the Day 30 visit.
- Length of surgery.
- Total time in OR.
- Occurrence of re-hospitalization, within 30 days of enrollment, including length of re-hospitalization (through 30 days post enrollment).
- Occurrence of post-surgical major bleeding, as defined by ISTH criteria (see Section 4.1), within 12 hours after the end of the initial surgery.
- Occurrence of re-operations for bleeding, including for surgical wound hematomas, within 12 hours after the end of the initial surgery.
- Change from baseline in TFPI activity post-administration of andexanet.
- Change from baseline in anti-IIa activity (only patients taking enoxaparin).

11.5.3. Statistical Methodology for Endpoint Analyses

All efficacy analyses will be performed on the efficacy analysis population. All hypothesis tests and CIs will be 2-sided with $\alpha=0.05$.

The primary endpoint, the proportion of patients who have effective hemostasis, will be summarized with a 95% CI.

The secondary endpoint, percent change in anti-fXa activity from baseline to the nadir for the evaluation period, will be assessed with a 2-sided 95% nonparametric CI for the median.

For the exploratory endpoints, counts data will be summarized by observed rates and associated 95% CIs. Continuous endpoints will be summarized by means or medians and associated 95% CIs.

11.6. Determination of Sample Size

Approximately 200 patients will be enrolled. After accounting for 10 to 25% attrition (e.g., canceled surgeries, discontinued and/or non-evaluable patients, or baseline anti-fXa activity analyzed by central laboratory less than the evaluability threshold), a sample size of 150 or 180 patients will provide an estimate of the proportion of achieving effective (excellent or good) hemostasis with a margin of error (half width of the 95% confidence interval) that is less than 8% or 7.3%, respectively. Additionally, with 150 to 180 patients, there will be 78% to 84% chance to observe a rare event with 1% occurrence rate.

11.7. Safety Endpoints and Summaries

Safety will be assessed by examining the following endpoints and analyzed in the Safety Analysis Population:

- AEs (including SAEs), vital signs, physical examinations, and clinical laboratory measurements.
- TEs within 30 days of enrollment, including those suspected and confirmed by adjudication.
- Centrally-adjudicated deaths within 30 days of enrollment, including all-cause mortality and cardiovascular mortality.
- Antibodies to FX, FXa, andexanet, and HCPs.

11.7.1. Adverse Events

Treatment-emergent adverse events, including preferred terms defined by the Medical Dictionary for Regulatory Activities (MedDRA), will be summarized by system organ class. Arterial and venous thromboembolic events, considered AESIs, will be summarized separately.

The number of events, the number of patients, and the percentage of patients who experienced at least 1 TEAE will be presented. The TEAEs that are considered by the Investigator to be related to the andexanet, TEAEs that lead to early withdrawals, and serious TEAEs will be summarized in the same manner. Frequent TEAEs, including preferred terms with an incidence rate of $\geq 5\%$, will also be summarized.

All potential post-surgical bleeding events will be assessed by the EAC and summarized descriptively, including whether patients were re-anticoagulated prior to the event. Postoperative major bleeding events will be additionally adjudicated by the EAC.

Concomitant medications will be coded using the World Health Organization (WHO) Drug Dictionary.

11.7.2. Thrombotic Events

All TEs will be assessed by the EAC and summarized descriptively, including whether patients were re-anticoagulated prior to the event.

11.7.3. Deaths

All deaths will be assessed by the EAC. Deaths due to cardiovascular causes (i.e., resulting from MI, sudden cardiac death, heart failure, stroke, cardiovascular procedures, cardiovascular hemorrhage, and other cardiovascular causes) will be classified as related to bleeding or non-hemorrhagic.

